## Title page

# **Whole-body photobiomodulation for muscle performance enhancement, attenuation of muscular damage and delayed onset muscle soreness in professional soccer athletes – randomized sham-controlled trial**

## Abstract

**Context:** Photobiomodulation (PBM) has recently been applied in sports to enhance physical performance and mitigate muscle damage and delayed-onset muscle soreness (DOMS). These effects may be particularly relevant when PBM is delivered to large body areas through whole-body irradiation. **Objective:** To evaluate the effects of whole-body PBM on muscle damage, DOMS, and muscle performance in professional soccer athletes undergoing a muscle damage induction protocol. **Methods:** A randomized, double-blind, sham-controlled trial was conducted with 30 professional soccer players from a Brazilian team. Participants were randomly allocated into three groups ( $n = 10$  each): (a) PBM-post, (b) PBM-pre, and (c) PBM-sham. Outcomes included serum creatine kinase (CK) levels, DOMS (numeric rating scale [NRS] and pain mapping [mapDOMS]), muscle performance (squat jump [SJ] and countermovement jump [CMJ]), and isometric dynamometry of the knee extensors. All groups received PBM irradiation (active or sham), followed by the muscle damage induction protocol, and subsequent PBM irradiation (active or sham). Assessments were performed at baseline, 24 h, 48 h, and 72 h post-induction. **Results:** CK levels significantly increased ( $p < 0.05$ ) at 24–72 h in the sham group and at 24–48 h in the PBM-post group. In contrast, the PBM-pre group showed no significant increase ( $p > 0.05$ ) across 24–72 h. For DOMS (NRS), the sham group

reported significant increases ( $p < 0.05$ ) from 24–72 h, the PBM-pre group only at 24 h, and the PBM-post group at no time point. DOMS assessed by mapDOMS showed no significant changes ( $p > 0.05$ ) across groups or time points. No significant differences ( $p > 0.05$ ) were observed in muscle performance outcomes among groups. **Conclusion:** Pre-exercise PBM provided protective effects against muscle damage (lower CK) and reduced DOMS at 48–72 h, while post-exercise PBM reduced DOMS consistently at all time points (24–72 h). Neither pre- nor post-exercise PBM improved or worsened muscle performance.

**Keywords:** CK; DOMS; light-emitting diode; low-level laser therapy; recovery

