### Creatine Kinase (CK)

The CK data in U/L did not follow a normal distribution, and a logarithmic transformation ( $\log_{10}$ ) was applied. After the transformation, the data showed a normal distribution and homogeneity of variances for conducting parametric tests. Repeated measures ANOVA revealed a moment interaction ( $F_{2,27} < 0.001$ ) and a moment versus treatment interaction ( $F_{2,27} < 0.001$ ). Tukey's post hoc test identified significant differences as shown in the table below:

[figure not shown]
**Table 5.** Mean values ( $\pm$ standard deviation) of creatine phosphokinase (CK) in U/L for the Sham, PBM-pre, and PBM-post groups at pre, 24h, 48h, and 72h after the muscle damage induction protocol:

| Groups   | CK pre                 | CK 24h                  | CK 48h                  | CK 72h                  |
|----------|------------------------|-------------------------|-------------------------|-------------------------|
| Sham     | 289.2 ( $\pm 209.94$ ) | 661.5 ( $\pm 477.24$ )* | 491.6 ( $\pm 285.44$ )* | 523.2 ( $\pm 343.15$ )* |
| PBM-pre  | 249.2 ( $\pm 112.28$ ) | 372.7 ( $\pm 190.58$ )  | 424.2 ( $\pm 248.90$ )  | 392.6 ( $\pm 215.23$ )  |
| PBM-post | 287.8 ( $\pm 199.09$ ) | 794.5 ( $\pm 763.80$ )* | 631.2 ( $\pm 512.08$ )* | 271.44 ( $\pm 133.27$ ) |

**Abbreviations:** PBM (photobiomodulation); CK (creatine phosphokinase). \* p-value  $< 0.05$  in two-way repeated measures ANOVA followed by Tukey's post hoc analysis.

Compared to the pre-moment of the muscle damage induction protocol, there was a significant increase in CK levels in the Sham group ( $p = 0.001$ ) and PBM-post group ( $p = 0.001$ ) at the moment 24h after, while in the PBM-pre group the increase was not significant ( $p = 0.285$ ). When comparing the pre-moment of the muscle damage induction protocol to 48h after, the Sham group had a significant increase in CK ( $p = 0.028$ ), as well as the PBM-post group ( $p = 0.015$ ), while the PBM-pre group did not show a significant increase ( $p = 0.131$ ). In the

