comparison between the pre-moment of the muscle damage induction protocol and 72h after, only the Sham group had a significant increase in CK ( $p = 0.010$ ), while the PBM-pre and PBM-post groups did not show significant increases ( $p = 0.506$ ;  $p = 1.000$ , respectively). In the comparison between groups for the respective CK assessment moments, there were no significant differences ( $p > 0.05$ ). The graphical representation of these results is in Figure 4.

**Figure 4.** Results for creatine phosphokinase (CK) at the evaluated time points (pre-moment of muscle damage induction protocol, 24h, 48h, and 72h after), and experimental groups (Sham, PBM-pre, PBM-post). Values presented in both log10-transformed and raw formats. Data expressed as mean ( $\pm$  standard error).

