Compared to the pre-moment of the muscle damage induction protocol, there was a significant increase in DOMS measured by the NRS in the Sham group ( $p < 0.001$ ) and PBM-pre group ( $p = 0.027$ ) at the moment 24h after, while the PBM-post group did not show a significant increase ( $p = 0.460$ ). In the comparison between the pre-moment of the muscle damage induction protocol and 48h after, the Sham group had a significant increase in DOMS (NRS) ( $p < 0.001$ ), while the PBM-pre and PBM-post groups did not show significant increases ( $p = 0.555$ ;  $p = 0.933$ , respectively). In the comparison between the pre-moment of the muscle damage induction protocol and 72h after, only the Sham group had a significant increase in DOMS ( $p = 0.027$ ), while the PBM-pre and PBM-post groups did not show significant increases ( $p = 0.999$ ;  $p = 0.993$ , respectively). In the comparison between groups for the respective moments of DOMS (NRS) assessment, there were no significant differences ( $p > 0.05$ ). The graphical representation of these results is in Figure 5.

**Figure 5.** Results for Delayed Onset Muscle Soreness (DOMS), measured by the Numeric Rating Scale (NRS) at the evaluated time points (pre-moment of muscle damage induction protocol, 24h, 48h, and 72h after), and experimental groups (Sham, PBM-pre, PBM-post). Data expressed as mean ( $\pm$  standard error).

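### The abstract claims lower CK and time-specific soreness benefits from within-arm changes, although the reported comparisons with Sham are non-significant at every time and are left out

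*Combined protocol and SAP*

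**What the plan says.** The Abstract's Conclusion states that "Pre-exercise PBM provided protective effects against muscle damage (lower CK"), adds reduced soreness at 48–72 h for the same arm, and continues: "while post-exercise PBM reduced DOMS consistently at all time points" (24–72 h). For CK and NRS, the Abstract's Results give only changes from each arm's own baseline. For CK, Sham rose at 24–72 h and PBM-post at 24–48 h, whereas "the PBM-pre group showed no significant increase".

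The body reports three kinds of result for these outcomes:

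- **Within-arm changes.** In the Creatine Kinase section, at 72 h "only the Sham group had a significant increase in CK". The NRS section follows the same pattern: "Compared to the pre-moment of the muscle damage induction protocol, there was a significant increase in DOMS measured by the NRS" in Sham and PBM-pre at 24 h, and in Sham alone at 48 h and 72 h.
- **Interaction.** The CK section reports a time effect "and a moment versus treatment interaction", printed as F2,27 < 0.001. The NRS section prints F2,27 = 0.044.
- **Arms compared at each time.** For CK: "In the comparison between groups for the respective CK assessment moments, there were no significant differences". For NRS: "In the comparison between groups for the respective moments of DOMS (NRS) assessment, there were no significant differences".

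The abstract includes neither the second nor the third kind for CK or NRS, although it does report the null comparison among groups for muscle performance. The Statistical Analysis Plan (Summary) and the Data Analysis section both name CK as the primary outcome.

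**The concern.** The conclusion reads a significant rise in Sham, together with a non-significant rise in a PBM arm, as an effect of PBM in that arm at that time. A difference in significance is not a significant difference. In a randomised sham-controlled trial, a treatment effect is a contrast with Sham.

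The within-arm rule also places effects badly. PBM-pre gets no soreness credit at 24 h because its own rise of 2.6 points was significant (p = 0.027). Yet its change relative to Sham is larger at 24 h (-2.5) than at 48 h (-2.0) or 72 h (-2.1), where it is credited.

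Readers will take lower CK and the listed soreness benefits as tested differences from Sham, in the part of the report most of them rely on.

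**Working it through.** **Inputs.** Table 5 (CK) and Table 6 (NRS) means and SDs, 10 per arm, and the p-values in the text. The values printed as F2,27 < 0.001 and F2,27 = 0.044 are read as p-values (an assumption).

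**1. Reproduce the NRS analysis.** The error mean square is not printed. For a Tukey test over all 12 cells with 81 df, MS = 10 × (d/q)², where d is the rise from baseline and q the studentized-range quantile for the reported p.

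- p = 0.027, d = 2.6, q = 5.064: MS = 2.64. This applies twice, to Sham at 72 h and PBM-pre at 24 h.
- p = 0.460, d = 1.7, q = 3.305: MS = 2.65.
- p = 0.555 (d = 1.6) and p = 0.933 (d = 1.1): MS = 2.65 each.

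The p-values 0.993 and 0.999 are too close to 1 to inform it. From the Table 6 means, the interaction sum of squares is 36.15, so the mean square is 36.15/6 = 6.025 and F(6,81) = 6.025/2.64 = 2.28, p = 0.044. This matches the reported value.

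**2. NRS change from baseline versus Sham.** SE = √(4 × 2.64/10) = 1.03, 81 df, sphericity assumed. Holm is taken over the six contrasts (for example 6 × 0.0014 = 0.008).

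| Contrast | Time | Difference (95% CI) | p | Holm p |
|---|---|---|---|---|
| PBM-post | 24 h | -3.4 (-5.4 to -1.4) | 0.001 | 0.008 |
| PBM-post | 48 h | -2.5 (-4.5 to -0.5) | 0.017 | 0.086 |
| PBM-post | 72 h | -1.8 (-3.8 to 0.2) | 0.084 | 0.13 |
| PBM-pre | 24 h | -2.5 (-4.5 to -0.5) | 0.017 | 0.086 |
| PBM-pre | 48 h | -2.0 (-4.0 to 0.04) | 0.055 | 0.13 |
| PBM-pre | 72 h | -2.1 (-4.1 to -0.1) | 0.044 | 0.13 |

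Four of six are nominally significant and one survives Holm. With 27 df instead of 81, the unadjusted p-values become 0.003, 0.022, 0.091 (PBM-post) and 0.022, 0.062, 0.051 (PBM-pre).

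**3. NRS adjusted for baseline.** Two-arm ANCOVA from summary statistics, common slope, 17 df. The within-person correlation is not reported. The pooled cell variance of Table 6 is 4.15, which implies an average of 1 - 2.64/4.15 = 0.36. The correlation with baseline at a given time may differ, so 0 and 0.7 are also shown (unadjusted p).

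| Contrast | Time | ρ = 0 | ρ = 0.36 | ρ = 0.7 |
|---|---|---|---|---|
| PBM-post | 24 h | 0.012 | 0.004 | 0.0002 |
| PBM-post | 48 h | 0.090 | 0.041 | 0.007 |
| PBM-post | 72 h | 0.33 | 0.19 | 0.065 |
| PBM-pre | 24 h | 0.11 | 0.048 | 0.005 |
| PBM-pre | 48 h | 0.16 | 0.076 | 0.014 |
| PBM-pre | 72 h | 0.19 | 0.096 | 0.019 |

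After Holm, none survives at 0, only PBM-post at 24 h survives at 0.36 (p = 0.023), and all but PBM-post at 72 h survive at 0.7.

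**4. NRS at the same time, unadjusted.** At 24, 48 and 72 h, PBM-post minus Sham is -2.7 (-4.6 to -0.8), -1.8 (-3.8 to 0.2) and -1.1 (-3.3 to 1.1). PBM-pre minus Sham is -1.9 (-4.2 to 0.4), -1.4 (-3.3 to 0.5) and -1.5 (-3.7 to 0.7).

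**5. CK (approximate).** The log10 means appear only in Figure 4, so Table 5 was converted by log-normal moments: σ² = ln(1 + (SD/mean)²), μ = ln(mean) - σ²/2. For PBM-pre versus Sham at 24 h, μ = 5.805 and 6.285, σ² = 0.232 and 0.419. The difference is -0.480 with SE √(0.651/10) = 0.255, so the ratio is 0.62 (0.36 to 1.06, 18 df).

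| Ratio to Sham | 24 h | 48 h | 72 h |
|---|---|---|---|
| PBM-pre | 0.62 (0.36–1.06) | 0.86 (0.52–1.43) | 0.79 (0.47–1.33) |
| PBM-post | 1.07 (0.54–2.13) | 1.15 (0.64–2.09) | 0.56 (0.34–0.92) |

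Baseline-adjusted p-values, for assumed correlation 0 to 0.7, are 0.085–0.026, 0.56–0.48 and 0.36–0.25 for PBM-pre, and 0.85–0.82, 0.63–0.53 and 0.030–0.004 for PBM-post. After Holm over six, PBM-pre at 24 h is 0.43–0.13, PBM-post at 72 h is 0.18–0.023, and all others are 1.0. The ratio furthest from 1 therefore belongs to PBM-post at 72 h, not to the arm credited with lower CK.

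**The case against.** The strongest defence is the interaction. It compares randomised arms and is reported as significant for both outcomes. Same-time comparisons do not use the baseline, whereas differences in change do, and several of those are nominally significant for NRS. CK is not empty either. Back-solving the CK error mean square gives inconsistent values (0.104 to 0.187 on the natural-log scale). Over that range the PBM-pre change versus Sham at 24 h has unadjusted p = 0.03 to 0.10, and PBM-post at 72 h has 0.0045 to 0.032.

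Much of this stands. The evidence is mixed, not nil, and non-significance with 10 per arm does not show absence of effect. It does not support the abstract, though. The interaction identifies neither arm nor time, the documents report no contrasts in change, and same-time comparisons of randomised arms do test an arm effect at that time.

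Three cautions apply to any replacement text:

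- The printed interaction values carry 2 and 27 df, whereas a 3 × 4 interaction has 6 and 81 under sphericity.
- No sphericity check is described. If epsilon were 0.9, 0.8 or 0.7, F = 2.28 would give p = 0.051, 0.059 or 0.069. For CK, the range above gives interaction p = 0.0004 to 0.023.
- The PBM-post CK mean at 72 h, 271.44, equals 2443/9, which hints at nine values if CK was recorded in whole units. With nine, the interval for 0.56 becomes 0.33 to 0.94, a small change.

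It can also be said that rewording alone would cure the misstatement. That is true, but the report would then contain no estimate of the effects it set out to measure.

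**Conclusion.** The concern holds and the conclusion must be corrected. This rests on the document's own text: within-arm changes are presented as treatment effects, and the null comparisons between arms are omitted.

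For CK, a PBM-pre benefit is not shown. For NRS, PBM-post at 24 h is the best supported effect. The claim for all time points is not shown at 72 h, and the PBM-pre claim at 48–72 h does not survive Holm at the implied correlation of 0.36, though it would at 0.7.

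The NRS figures assume the back-solved error term and, for the changes in step 2, sphericity. The CK figures depend on a log-normal conversion and are approximate, but the verdict does not depend on them.

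**What to change.** Leave the Statistical Analysis Plan (Summary) and Data Analysis sections as the record of the original plan, and make these changes:

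1. Add a Results subsection headed *Post hoc between-arm contrasts (specified after results were known)*. Give PBM-pre versus Sham and PBM-post versus Sham at 24, 48 and 72 h, for log10 CK and for NRS, adjusted for baseline, with 95% CIs and one stated multiplicity adjustment (for example Holm over the six contrasts of each outcome). State that within-arm changes are descriptive.
2. Confirm the interaction p-values, their degrees of freedom and sphericity from the software output. Then add to the abstract's Results:

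> Time-by-treatment interaction: CK p < 0.001, NRS p = 0.044. No between-group comparison of CK or NRS at any single time was significant.

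3. Replace the abstract's conclusion, keeping its first sentence only if step 2 bears it out:

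> Time courses of CK and NRS differed among the three arms. No reported per-time between-group comparison was significant. Post hoc baseline-adjusted contrasts with Sham were [estimates and 95% CIs, whatever they show]. No effect on muscle performance was shown.

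The cost is a re-run on existing data plus rewording. The conclusion may be less favourable, the new contrasts carry only post hoc weight with wide intervals at 10 per arm, and Holm gives up some power compared with unadjusted contrasts.

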### STATISTICAL ANALYSIS PLAN (SUMMARY)

Primary endpoint: Serum CK levels (U/L) over time.

Secondary endpoints: DOMS (NRS and mapDOMS), SJ and CMJ jump heights (cm), and isometric knee extensor force (kgf).

Statistical tests:

- Normality (Shapiro–Wilk) and homogeneity (Levene).
- Two-way repeated measures ANOVA with Tukey post hoc (parametric).
- Friedman and Kruskal–Wallis (nonparametric when assumptions not met).
- Significance level:  $\alpha = 0.05$ .

Software: IBM SPSS Statistics v20.0.

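### The abstract's Conclusion interprets the primary endpoint (CK) for PBM-pre only and describes PBM-post by soreness alone, so it is incomplete and uneven on CK

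*Combined protocol and SAP*

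**What the plan says.** The Statistical Analysis Plan (Summary) names one primary endpoint: "Primary endpoint: Serum CK levels (U/L) over time". The Data Analysis section confirms that CK is primary. DOMS, jump height and knee extensor force are secondary.

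The abstract's Conclusion treats the two active arms differently:

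- PBM-pre: "Pre-exercise PBM provided protective effects against muscle damage (lower CK) and reduced DOMS at 48–72 h".
- PBM-post: "while post-exercise PBM reduced DOMS consistently at all time points" (24 to 72 h), with no mention of CK.
- Both arms: a joint sentence that muscle performance was neither improved nor worsened.

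The abstract's Results do cover CK in all three arms. They place the significant rises "at 24–72 h in the sham group and at 24–48 h in the PBM-post group" and report none for PBM-pre. The section Creatine Kinase (CK) gives the means, SDs and p-values for every arm and time point, then adds: "In the comparison between groups for the respective CK assessment moments, there were no significant differences".

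**The concern.** The Conclusion covers both active arms on soreness and on performance, which are secondary, but only one of them on the primary endpoint. The missing statement is the less favourable one: by the authors' own criterion of change from baseline, PBM-post showed the same pattern as Sham on the first two days.

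Someone who reads only the Conclusion learns that post-exercise irradiation helped soreness. They do not learn what happened to muscle damage in that arm, which is the trial's main question. They may also take the CK statement for PBM-pre as a demonstrated advantage over Sham, which the between-group comparison does not provide.

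**Working it through.** **1. The authors' own figures.** Within-arm p-values against baseline, from the text around Table 5:

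| Arm | 24 h | 48 h | 72 h |
|---|---|---|---|
| Sham | 0.001 | 0.028 | 0.010 |
| PBM-pre | 0.285 | 0.131 | 0.506 |
| PBM-post | 0.001 | 0.015 | 1.000 |

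These agree with the asterisks in Table 5. Applied evenly, the within-arm rule gives: PBM-pre, no significant rise at any time; PBM-post, a significant rise at 24 and 48 h as in Sham, and none at 72 h. The Conclusion carries the first of these and omits the second.

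**2. Size of the omitted result.** Table 5 means in U/L, with the ratio to the arm's own baseline in brackets:

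| Arm | Pre | 24 h | 48 h | 72 h |
|---|---|---|---|---|
| Sham | 289.2 | 661.5 (2.29) | 491.6 (1.70) | 523.2 (1.81) |
| PBM-pre | 249.2 | 372.7 (1.50) | 424.2 (1.70) | 392.6 (1.58) |
| PBM-post | 287.8 | 794.5 (2.76) | 631.2 (2.19) | 271.44 (0.94) |

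**3. Difference from Sham.** Two approximations from the Table 5 means and SDs, taking n = 10 per arm, with no adjustment for multiplicity or baseline:

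- Raw scale (Welch): difference ± t × √(SD₁²/10 + SD₂²/10). For PBM-post at 24 h the standard error is √(763.80²/10 + 477.24²/10) ≈ 285.
- Log scale, since the analysis used log10: geometric mean ≈ mean/√(1 + CV²), where CV = SD/mean. This assumes lognormal data. For PBM-post at 24 h, CV = 763.80/794.5 = 0.96, giving about 573 against 536 in Sham, a ratio of 1.07.

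| Comparison with Sham | Raw difference, U/L (95% CI) | Geometric mean ratio (95% CI) |
|---|---|---|
| PBM-post 24 h | +133.0 (−474 to 740) | 1.07 (0.54–2.13) |
| PBM-post 48 h | +139.6 (−258 to 537) | 1.15 (0.64–2.09) |
| PBM-post 72 h | −251.8 (−506 to 3) | 0.56 (0.34–0.92) |
| PBM-pre 24 h | −288.8 (−644 to 66) | 0.62 (0.36–1.06) |
| PBM-pre 48 h | −67.4 (−319 to 185) | 0.86 (0.52–1.43) |
| PBM-pre 72 h | −130.6 (−403 to 142) | 0.79 (0.47–1.33) |

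Every raw-scale interval includes zero. On the log scale only PBM-post at 72 h excludes 1. That is one of six unadjusted approximations, and it does not displace the reported finding of no significant between-group difference.

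**4. The 72 h PBM-post mean.** It is printed as 271.44; every other CK mean in Table 5 has one decimal. A mean of ten whole-number values needs at most one decimal, whereas 2443/9 = 271.44. In Table 4, PBM-post age and years of practice also fit a denominator of nine: 191/9 = 21.22 and 103/9 = 11.44. Against this, the PBM-post phototype counts sum to ten (3 + 5 + 1 + 1 + 0), the reported denominator degrees of freedom are 27 = 30 − 3, and the Results state that nobody dropped out. Nine values is therefore only an inference, and it assumes CK was recorded in whole units. If a tenth value were missing, it would have to exceed 10 × 392.6 − 2443 = 1483 U/L before PBM-post lost the lowest mean at 72 h.

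**The case against.** The strongest reply is that nothing is hidden. The abstract's Results state the PBM-post rise two sentences or so before the Conclusion, and the CK section prints every mean, SD and p-value. This stands: the fault is an incomplete Conclusion, and a charge of concealing the primary endpoint would not be fair.

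A second reply is that the root problem is inferring effects from within-arm tests. Once that is corrected, PBM-pre loses its CK claim and the imbalance disappears. This is partly right, and the fix should cover both arms for that reason. But changing the type of test would not by itself put a PBM-post CK statement into the Conclusion.

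Three stronger readings are tempting, and the documents do not support them:

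- **That PBM-post raised CK above Sham at 24–48 h.** The raw means are 20% and 28% higher (794.5/661.5 and 631.2/491.6), but the intervals are very wide. On the log scale the ratios are about 1.07 and 1.15, and the authors report no between-group difference.
- **That the Conclusion contradicts Table 5.** By the within-arm rule PBM-pre is the only arm with no significant rise at any time, so its CK statement follows from that rule. Table 5 holds no soreness data, and the Conclusion credits PBM-pre with both CK and soreness effects. It does not divide damage and soreness between the two timings.
- **That the largest CK departure from Sham is in PBM-post.** This holds only on a ratio scale (0.56 at 72 h against 0.62 for PBM-pre at 24 h). In U/L, the stated unit of the endpoint, PBM-pre at 24 h is further from Sham (−288.8 against −251.8).

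**Conclusion.** The point holds as an omission in the Conclusion. The primary endpoint is interpreted for one of two active arms. The result left out is a significant rise from baseline at 24 h (p = 0.001) and 48 h (p = 0.015), as in Sham, with no difference from baseline at 72 h (p = 1.000). The between-group comparison shows no CK protection for either timing. With ten per arm and intervals this wide, that is absence of evidence for a difference and not evidence that the arms are alike.

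The omission itself rests only on the printed text and p-values. The intervals and ratios above are approximations from summary data, used to judge how far the figures can be pressed. The 72 h statement for PBM-post also depends on the count behind 271.44, which the documents leave open.

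**What to change.** Revise the abstract's Conclusion as follows:

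1. Report CK for both active arms. For PBM-post, say that CK rose significantly from baseline at 24 and 48 h, as in Sham, and was not significantly above baseline at 72 h.
2. For both active arms, say that CK did not differ significantly from Sham at any time point, so the between-group comparison shows no CK protection for pre- or post-exercise irradiation. The wording "Pre-exercise PBM provided protective effects against muscle damage (lower CK") should be limited to what was tested: no significant within-arm rise.
3. Before stating the 72 h result, confirm how many values lie behind 271.44. If there were nine, report the count in Table 5 and reconcile it with the statement that all 30 athletes completed every procedure.

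The cost is one or two sentences and one data check, with no new analysis. The Conclusion becomes less favourable to both active arms.

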## Randomization and Allocation Concealment

The randomization was conducted using the website randomization.com, and the participants were allocated into three groups of ten individuals each. To ensure allocation concealment, sealed opaque envelopes were used, containing the randomly assigned interventions: PBM-post, PBM-pre, and PBM-Sham. Only one researcher (therapist 1) was involved in this process, being responsible for applying PBM to all participants. This researcher was blinded to the other assessments in the study, which were conducted by therapist 2. Participants were unaware of which intervention was applied during the study.

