### 3.7 Sample Size Calculation

The sample size ( $n=30$ ) was calculated a priori using GPower 3.1 software. It considered 3 groups, 4 assessment time points (immediately after the muscle damage induction protocol, and at 24h, 48h, and 72h after), a minimum effect size of 0.25, a test power of 80%, and a significance level of 5%, for comparisons through two-way repeated measures analysis of variance.

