## Data Analysis

Data analysis was conducted by a researcher blinded to participant group allocation. The primary outcome of the study was considered the muscle damage measured by CK levels.

The data were descriptively analyzed using mean and standard deviation. The independent variables were the experimental conditions (Sham, PBM-pre, and PBM-post) and assessment times pre, 24h, 48h, 72h after the muscle damage induction protocol. Normality and homoscedasticity assumptions were tested beforehand using the Shapiro-Wilk W Test and Levene test, respectively. The dependent variables included CK, DOMS, height of jumps in Squat Jump (SJ) and Counter Movement Jump (CMJ), and isometric manual dynamometry of the femoral quadriceps (kgf).

Two-way repeated measures analysis of variance (ANOVA) was conducted (considering pre, 24h, 48h, and 72h after the muscle damage induction protocol) followed by Tukey's post hoc test when the data showed normal distribution and variance homogeneity. In cases where the data did not present normal distribution, a logarithmic transformation (log10) was adopted, and normality and variance homogeneity were verified again for parametric tests. If the data did not meet the assumptions of normality and variance homogeneity, non-parametric tests such as Friedman's ANOVA (intragroup analyses) and Kruskal-Wallis (intergroup analyses) were employed. The significance level was set at 5%. Statistical analysis was performed using a statistical software (SPSS Statistics for Windows version 20.0, IBM, Chicago, IL, United States).

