## RESULTS

Thirty male professional football players (high level) from the same team were recruited and completed all procedures of this study. Therefore, there were no dropouts, and intention-to-treat analysis was not necessary. Anthropometric data are described in Table 4. No adverse effects were reported during the study.

**Table 4.** Anthropometric data of the investigated athlete sample. Values in mean ( $\pm$  standard deviation):

| Groups | Age (years)  | Body Mass (kg) | BMI
(kg/m^2) | Years of Practice | Fitzpatrick
Phototype          |
|---------------|---------------------|-----------------------|-----------------------------------|--------------------------|-------------------------------------------|
| Sham   | 18.70 ( $\pm$ 0.82) | 76.03 ( $\pm$ 13.27)  | 22.62 ( $\pm$ 2.10)               | 9.60 ( $\pm$ 1.77)       | Type I: 2,
Type II: 0,
Type III: 3, |

|                 |                      |                      |                      |                      |                                                                       |
|-----------------|----------------------|----------------------|----------------------|----------------------|-----------------------------------------------------------------------|
|                 |                      |                      |                      |                      | Type IV: 3,
Type V: 2                                              |
| PBM-pre  | 20.50 ( $\pm 4.30$ ) | 70.43 ( $\pm 4.90$ ) | 23.07 ( $\pm 0.94$ ) | 11.30 ( $\pm 3.74$ ) | Type I: 2,
Type II: 2,
Type III: 3,
Type IV: 2,
Type V: 1 |
| PBM-post | 21.22 ( $\pm 7.44$ ) | 76.13 ( $\pm 8.03$ ) | 23.48 ( $\pm 1.73$ ) | 11.44 ( $\pm 3.46$ ) | Type I: 3,
Type II: 5,
Type III: 1,
Type IV: 1,
Type V: 0 |

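### The abstract concludes that PBM neither improved nor worsened muscle performance, but this rests on non-significance with 10 athletes per arm; the data are inconclusive, not null

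*Combined protocol and SAP*

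**What the plan says.** The abstract's results report only that no significant differences (p > 0.05) "were observed in muscle performance outcomes among groups". Its conclusion then reads: "Neither pre- nor post-exercise PBM improved or worsened muscle performance".

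The Statistical Analysis Plan (Summary) lists SJ, CMJ and isometric knee-extensor force as secondary endpoints. Data Analysis plans a two-way repeated measures ANOVA with Tukey post hoc tests at the 5% level. Section 3.7 sizes the trial for "a minimum effect size of 0.25, a test power of 80%, and a significance level of 5" per cent. Under Randomization and Allocation Concealment, "the participants were allocated into three groups of ten individuals each". All 30 athletes completed the study.

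No section sets an equivalence or non-inferiority margin. The results sections for SJ, CMJ and dynamometry give arm means, SDs and ANOVA results. They give no active-minus-Sham difference and no confidence interval. The time-by-treatment results are 0.834 (SJ), 0.127 (CMJ) and 0.486 (dynamometry). They are printed as F values but are evidently p-values, and are read that way here.

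**The concern.** A p-value above 0.05 says that a difference was not detected. It does not show that the difference is small. The conclusion rules out both benefit and harm, and that needs intervals narrow enough to exclude effects that matter. The reader is given none.

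Performance enhancement is named in the trial's title, and the sentence stands in the abstract's conclusion. Readers will probably take it as a finding of no benefit and no harm.

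A second, narrower issue concerns protection. If the damage protocol produced little loss of performance in Sham, there was little loss for PBM to prevent or reverse.

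**Working it through.** **1. The plan's own sample size.** For a within-between interaction with 3 groups, 4 times, f = 0.25 and N = 30, assume a correlation of 0.5 between repeated measures and no sphericity correction (neither is stated). Then lambda = f² × N × m / (1 − rho) = 0.0625 × 30 × 4 / 0.5 = 15, with 6 and 81 df, and power is 0.809. So N = 30 is reproduced. This is power to detect an interaction of that size. It does not allow pairwise differences to be ruled out.

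A pairwise comparison at one time, with 10 per arm and 80% power, can detect (1.960 + 0.842) × SD × √(2/10). SD is the root mean square of the post-induction SDs in Tables 8 to 10: 5.25 cm (SJ), 5.23 cm (CMJ) and 9.51 kgf (force). The results are 6.58 cm, 6.55 cm and 11.91 kgf, or 16.7%, 16.2% and 21.6% of the average Sham mean.

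**2. Single-time intervals.** Half-width = t(18; 0.975) × √[(SD₁² + SD₂²)/10], with t = 2.101. Example, SJ, PBM-pre minus Sham at 72 h: 2.101 × √[(4.13² + 7.08²)/10] = 5.45 cm. The difference is 40.32 − 39.12 = +1.20 cm, so the interval is −4.25 to 6.65 cm, and the half-width is 5.45/39.12 = 13.9% of the Sham mean.

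There are 24 contrasts (3 outcomes, 2 active arms, 4 post-induction times):

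| Outcome | Half-width, % of Sham mean | Most extreme limits |
|---|---|---|
| SJ | 9.3 to 14.5 | −14.5% to +17.0% |
| CMJ | 9.3 to 14.3 | −14.3% to +20.3% |
| Force | 14.8 to 18.4 | −20.0% to +33.5% |

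In units, half-widths are 3.7 to 5.8 cm for jumps and 8.1 to 10.4 kgf for force. All 24 intervals include 0. Study Design places the immediate test before the second irradiation, so the three PBM-post contrasts at that time precede that arm's active treatment. Leaving them out does not change the extreme limits, and raises only the CMJ minimum half-width, from 9.3% to 9.7%.

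**3. Change from pre.** Arms differed at baseline. PBM-post minus Sham was 37.04 − 39.80 = −2.76 cm (SJ), 38.29 − 40.86 = −2.57 cm (CMJ) and 59.53 − 50.41 = +9.12 kgf (force). The 72 h force gap of +8.47 kgf therefore becomes (63.18 − 59.53) − (54.71 − 50.41) = −0.65 kgf as a difference in change.

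The variance of change in one arm is SD_pre² + SD_t² − 2 × rho × SD_pre × SD_t. Rho is not given and must be assumed. Example, CMJ, PBM-pre minus Sham at 72 h, rho = 0.8: variances 8.92 (Sham) and 19.51 (PBM-pre); half-width 2.101 × √(28.43/10) = 3.54 cm. The difference is (42.98 − 41.17) − (40.35 − 40.86) = +2.32 cm, so the interval is −1.22 to 5.86 cm.

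| Assumed rho | Jumps, half-width, % of Sham baseline | Force, half-width, % of Sham baseline |
|---|---|---|
| 0.5 | 9.4 to 14.5 | 20.9 to 22.5 |
| 0.8 | 6.0 to 9.2 | 13.9 to 15.2 |
| 0.9 | 4.3 to 6.7 | 10.5 to 12.1 |

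At rho = 0.9 the most extreme limits are still about −9% to +12% for jumps and −22% to +13% for force.

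**4. Sham change from pre** (immediately after, 24, 48, 72 h):
- SJ: −0.4, −3.1, +0.8, −1.7%
- CMJ: −0.9, −2.3, +0.6, −1.2%
- Force: +6.8, +10.3, +12.0, +8.5%

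**The case against.** The sponsor can fairly say that this is an ordinary difference-testing design, that performance is secondary, and that the abstract prints the non-significance result just before the conclusion. The absence of a margin is not in itself a defect. All of that stands. It makes the point modest, but it does not turn p > 0.05 into evidence of no effect.

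Single-time contrasts also mix baseline gaps with any effect, and change-based intervals for jumps could be much narrower if the within-athlete correlation is high. This stands too, and is why the whole range is shown. Even the narrowest case leaves sizeable limits.

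Three stronger readings are tempting, and the documents do not support them:

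- *Sham lost no function.* Six of the eight Sham jump means fell below pre, by up to 3.1%. Calling that no loss repeats the error under criticism. Force rose on average, but from a baseline with SD 14.98 (9.61 to 11.14 later), and no post hoc difference was significant. Only little mean deficit can be claimed.
- *The model failed, so performance could not be tested.* Sham CK rose from 289.2 to 661.5 U/L and soreness from 0.60 to 5.70 at 24 h. A small performance deficit limits inference about protection or restoration. Enhancement and harm need no deficit, and those are what the quoted sentence addresses.
- *Some effects are real.* At rho = 0.9, four of the 24 change intervals just exclude 0: SJ and CMJ for PBM-post at 72 h (favourable), and force for both active arms at 24 h (unfavourable). That correlation is assumed, there is no multiplicity adjustment, and the reported interactions are not significant.

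**Conclusion.** The concern holds as a matter of inference and wording. The conclusion claims no effect in either direction on non-significance alone, and the published means and SDs leave the question open. Half-widths are about 9 to 15% for jumps and 15 to 18% for force at single times. These are plus-or-minus figures; full widths are about 19 to 37%. For change from pre they run from 4 to 15% for jumps and from 10 to 23% for force over correlations of 0.9 down to 0.5.

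The figures assume 10 analysed athletes per arm at every time, two-sided 95% t intervals and no multiplicity adjustment. The correlation has to come from the trial data. The document does not say what size of difference matters to these athletes, so the result is inconclusive in both directions.

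**What to change.** - Replace the sentence in the abstract's conclusion with: *no significant between-arm difference in performance was detected; meaningful benefit or harm cannot be excluded.*
- For SJ, CMJ and dynamometry, report each active-minus-Sham difference, adjusted for baseline, with its 95% interval. The athlete-level data supply the correlation that had to be assumed here.
- State that Sham showed little mean performance deficit, so protection of performance could not be adequately assessed.

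An equivalence margin should not be added now. The results are known, so it could not count as fixed in advance.

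The cost is a short reanalysis of existing data and some rewording. The downside for the sponsor is a less firm conclusion.
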